4.2 Exclusion Criteria

- 4.2.1. Prior complete course up to 5 Gy of radiotherapy to the pelvis.
- 4.2.2. Pregnant or lactating woman. Women of childbearing potential who have not undergone a hysterectomy with either a positive or no pregnancy test at baseline. Women / men of childbearing potential not using a reliable and appropriate contraceptive method (oral, injectable, or implantable hormonal contraceptive; tubal ligation; intra-uterine device; barrier contraceptive with spermicide; or vasectomized partner).
- 4.2.3. Treatment for other carcinomas within the last five years, except cured

non-melanoma skin and treated in-situ cervical cancer.

[figure not shown]
- 4.2.4 Patients with uncontrolled intercurrent illness including, but not limited to, ongoing or requiring IV antibiotics, cardiac disease NYHA class III or IV, unstable angina pectoris, unstable cardiac arrhythmia or tachycardia (heart rate > 100 beats/minute), or psychiatric illness/ social situations that would limit compliance with the study requirements are excluded.
- 4.2.5 Other serious uncontrolled medical conditions that the investigator feels might compromise study participation.
- 4.2.6 Major surgery within 4 weeks of the start of study treatment.
- 4.2.7 Prior unanticipated severe reaction to fluoropyrimidine therapy or known hypersensitivity to 5-fluorouracil or capecitabine or curcumin.
- 4.2.8 Concurrent use of coumadin other than low dose (1 mg) coumadin used for line patency. Patients on coumadin must be changed to Lovenox at least 1 week prior to starting capecitabine.
- 4.2.9 Concurrent use of cimetidine, allopurinol, or aluminium hydroxide and magnesium hydroxide-containing antacids such as Maalox.
- 4.2.10 Sorivudine and brivudine use within 4 weeks of the start of study treatment.

4.3 Prohibited Medications

Aluminum hydroxide- and magnesium hydroxide-containing antacids such as Maalox should not be used during this study because they increase the AUC and Cmax of capecitabine. Because clinically significant increases in prothrombin time (PT) and INR in patients who were stabilized on anticoagulants have been shown, patients on Coumadin® must be changed to Lovenox® at least 1 week prior to starting capecitabine. Low dose (1 mg) Coumadin® is allowed. Patients on phenytoin must have their phenytoin and albumin levels checked weekly during chemoradiation. Vaccination with live vaccines should not be instituted during treatment with capecitabine.

- 5.2.4 Dose: CTV1 will be treated to a dose of 45 Gy. This will be followed by a boost to CTV2 with a dose of 5.4 Gy. At the discretion of the treating radiation oncologist, up to an additional 3.6 Gy may be administered during the boost. All plans will be generated using 3D conformal techniques. At the discretion of the radiation oncologist, an intensity-modulated radiation therapy (IMRT) plan may be generated.
- 5.2.5 Fractionation: Radiotherapy will be delivered in 180 cGy once daily fractions for 28 fractions.
- 5.2.6 Dose constraints: Dose to the femoral heads will be limited to 50 Gy. The volume of small bowel getting > 45 Gy will be minimized. Dose heterogeneity will be less than 10%.
- 5.2.7 Radiotherapy will be interrupted for treatment related > Grade 2 non-hematological toxicity until it resolves to grade 1, then continued. If radiotherapy is interrupted, then capecitabine will also be interrupted. Please note that for any event which is apparent at baseline, the interruption will apply according to the corresponding shift in toxicity grade if the investigator feels it is appropriate (e.g. if a patient has grade 1 asthenia at baseline which increases to grade 2 during treatment, this will be considered as a shift of 1 grade and treated as a grade 1 toxicity for radiation interruption purposes).

5.3 Chemotherapy

5.3.1 Capecitabine

Capecitabine will be given at 825 mg/m² PO BID only on days of radiation (Monday through Friday). Dose adjustment of capecitabine will be made as needed (see 5.3.1.3).

5.3.1.1 Cautions when used with other medications

5.3.1.1.1 Concurrent use of coumadin other than low dose (1 mg) coumadin used for line patency is contraindicated. Patients on coumadin must be changed to Lovenox at least 1 week prior to starting capecitabine.

5.3.1.1.2 Increased phenytoin plasma concentrations have been reported during concomitant use of Capecitabine with phenytoin, suggesting a potential interaction. Patients taking phenytoin concomitantly with Capecitabine should be monitored weekly for increased phenytoin plasma concentrations and associated clinical symptoms.

5.3.1.1.3 Allopurinol. Oxpurinol, a metabolite of allopurinol, can potentially interfere with 5-FU anabolism via orotate phosphoribosyltransferase. Although this was originally used as a strategy to protect normal tissues from 5-FU-associated toxicity, further laboratory studies suggested possible antagonism of the anticancer activity of 5-FU in some tumor models. If a patient is receiving allopurinol, the need for taking this medicine should be ascertained. If possible, allopurinol should be discontinued prior to starting on this regimen, and another agent substituted for it.

5.3.1.1.4 Cimetidine: Because cimetidine can decrease the clearance of 5-FU, patients should not enter on this study until the cimetidine is discontinued. Ranitidine or a drug from another anti-ulcer class can be substituted for cimetidine if necessary.

5.3.1.1.5 Sorivudine and Brivudine: A metabolite of the above two investigational antiviral agents, 5-bromovinyluracil, is a potent inhibitor of dihydropyrimidine dehydrogenase, the enzyme that catabolizes 5-FU. Patients should not receive concurrent therapy with either of these antiviral agents while receiving capecitabine. If a patient has received prior sorivudine or brivudine, then at least four weeks must elapse before the patient receives capecitabine therapy.

5.3.1.2 Dosing

Capecitabine should be given approximately 12 hours apart (morning and evening), and taken within 30 minutes after the ingestion of food with approximately 200 mls of water (not fruit juices).

5.3.1.3 Dose modification guidelines of Capecitabine

Dose Modifications:

For any event which is apparent at baseline, the dose modifications will apply according to the corresponding shift in toxicity grade if the investigator feels it is appropriate (e.g. if a patient has grade 1 asthenia at baseline which increases to grade 2 during treatment, this will be considered as a shift of 1 grade and treated as a grade 1 toxicity for dose modification purposes).

Capecitabine treatment interruptions are regarded as lost treatment days and missed doses should not be replaced; the planned treatment schedule should be maintained. Once a dose has been reduced it should not be increased at a later time.

Toxicity

NCI Grade (a) (Value)

Neutropenia

Capecitabine will be held for >grade 2 neutropenia. Capecitabine can be restarted at 75% of the dose after recovery of neutropenia to grade 1. Patients will be removed from the study if they do not recover from the neutropenia.

Neutropenic fever

(grade 4 neutropenia and grade 2 fever) Interrupt capecitabine until resolved to grade 0, then continue at 75% of starting dose. Patients will be removed from the study if they do not

recover from the neutropenic fever.

Other hematological toxicities

No dose reductions or interruptions will be required for anemia as it can be satisfactorily managed by transfusions, if necessary.

Diarrhea [all; stools/day > pretreatment]

- 1 (2-3 stools/day) : Maintain dose
- 2 (4-6 stools/day) Interrupt until grade 0-1, continue according to number of appearances
 - 1st : 75% of starting dose.
 - 2nd : 50% of starting dose.
 - 3rd : 50% of starting dose.
- 3 (7-9 stools/day) Interrupt until grade 0-1, continue according to number of appearances
 - 1st : 75% of starting dose.
 - 2nd : 50% of starting dose.
 - 3rd : 50% of starting dose.
- 4 (10 stools/day) Interrupt until grade 0-1, then continue at 50% of starting dose.

Hand-Foot Syndrome

- 1 Maintain dose
- 2 Interrupt until grade 0-1, then continue at 75% of starting dose.
- 3 Interrupt until grade 0-1, then continue at 50% of starting dose.
- 4 (not applicable)

Other non-hematological toxicity

For toxicities which are considered by the Investigator unlikely to develop into serious or life-threatening events and which do not result in a delay or interruption of therapy (e.g. alopecia, altered taste etc.), treatment will be continued at the same dose without reduction or interruption.

- 1 Maintain dose
- 2 Interrupt until grade 0-1, continue according to number of appearances of same toxicity
 - 1st : 75% of starting dose.
 - 2nd : 50% of starting dose.
 - 3rd : 50% of starting dose.
- 3 Interrupt until grade 0-1, continue according to number of appearances of same toxicity
 - 1st : 75% of starting dose.
 - 2nd : 50% of starting dose.
 - 3rd : 50% of starting dose.
- 4 Interrupt until grade 0-1, then continue at 50% of starting dose.

a. National Cancer Institute Common Toxicity Criteria Version 3.0, see Appendix B.

5.3.1.4 Special Instructions Regarding Treatment of Toxicity;

5.3.1.4.1 Grade 2/3 Hand-Foot Skin Reaction

Treat symptomatically (recommended use of emollients).

The use of vitamin B6 Pyridoxine has been reported to be of possible benefit and is permitted for symptomatic or secondary prophylactic treatment of hand-foot skin reaction.

5.3.1.4.2 Neutropenia

When the ANC has recovered to 1,500/mm³ and fever or infection has resolved, the patient may restart treatment, with capecitabine at 75% of the starting dose if the patient had > grade 2 neutropenia, and at 100% of the starting dose if the patient did not have > grade 2 neutropenia.

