4.0 Patient Eligibility

4.1 Inclusion Criteria

- 4.1.1. All patients must have clinical stage T3,4 N0,1,2 or T2N1,2 adenocarcinoma of the rectum. Patients will be clinically staged using endorectal ultrasound, pelvic CT or MRI, and physical examination.
- 4.1.2. Histology must be confirmed with review by the Department of Pathology at MDACC.
- 4.1.3. All patients must have no distant metastatic disease in the liver, peritoneum, lungs, or paraaortic lymph nodes.
- 4.1.4. Patients must have a performance status (Karnofsky scale) of 70% or greater.
- 4.1.5. Patients must be \geq 18 years of age.
- 4.1.6. Patients must have ANC > 1200 cells/mm³, platelets $> 100,000$ /mm³, total serum bilirubin < 2 mg/dl, BUN < 30 mg/dl, creatinine < 1.5 mg/dl or creatinine clearance > 50 cc/min (estimated as calculated with Cockcroft-Gault equation).

Creatinine Clearance (men) = $\{(140 - \text{age}) \times \text{lean body weight (in kg.)}\} / \{\text{Plasma creatinine (mg/dl)} \times 72\}$

Creatinine Clearance (women) = $0.85 \times \{(140 - \text{age}) \times \text{lean body weight (in kg.)}\} / \{\text{Plasma creatinine (mg/dl)} \times 72\}$
- 4.1.7. Patients must have signed informed consent indicating that they are aware of the investigational nature of the study, and are aware that participation is voluntary. Patients must also agree to refrain from use of additional herbal supplements during the course of the study.
- 4.1.8. Postmenopausal woman must have been amenorrheic for at least 12 months to be considered of non-childbearing potential. Patients will agree to continue contraception for 30 days from the date of the last study drug administration. Sexually active males must practice contraception during the study.

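### Capecitabine restart rules after neutropenia are inconsistent for patients already dose-reduced, and possibly after neutropenic fever; the restart count also exceeds the entry limit

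*Combined protocol and SAP*

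**What the plan says.** The starting dose is in section 5.3.1: "Capecitabine will be given at 825 mg/m² PO BID only on days of radiation".

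Section 5.3.1.3 gives the general dose-modification rules:
- A limit stated ahead of the individual toxicities: "Once a dose has been reduced it should not be increased at a later time".
- Neutropenia: "Capecitabine will be held for >grade 2 neutropenia", and then "Capecitabine can be restarted at 75% of the dose after recovery of neutropenia to grade 1". Patients whose neutropenia does not recover leave the study; no count or time limit is attached.
- Neutropenic fever, defined there as grade 4 neutropenia with grade 2 fever: "Interrupt capecitabine until resolved to grade 0, then continue at 75% of starting dose".
- A baseline clause lets the investigator, where judged appropriate, apply modifications by the shift from the baseline toxicity grade.

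Section 5.3.1.4.2, under the special instructions on toxicity, covers neutropenia again. Its recovery condition is "When the ANC has recovered to 1,500/mm³ and fever or infection has resolved". Once that is met, "the patient may restart treatment, with capecitabine at 75% of the starting dose if the patient had > grade 2 neutropenia"; a patient whose neutropenia was not above grade 2 restarts at 100% of the starting dose.

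For entry, section 4.1.6 says "Patients must have ANC > 1200" cells/mm³.

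**The concern.** The same event is governed in two places that do not cross-refer and do not use the same terms. They differ on the reference dose (an unspecified dose against the starting dose). They express recovery differently (a toxicity grade against an absolute count). Only one of them carries the sentence barring later increases. A site holding a patient for neutropenia has no stated order of precedence.

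What is at stake is the re-dosing of a cytotoxic drug after toxicity. The patients for whom the sections diverge on dose have, by construction, already been reduced for another toxicity. Two sites, or two clinicians at one site, could each follow a section of the protocol and give the same patient different doses. One of those doses would breach a sentence of the protocol itself.

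A second issue is the count. The restart count is higher than the count accepted for enrolment, while the removal sentence does not say what counts as recovery.

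**Working it through.** The protocol states no calculated figure on this point, so there is nothing to reproduce. The check applies each rule to the same patient.

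**Inputs.** Starting dose 825 mg/m² twice daily (5.3.1). A current dose of 75% or 50% of starting can be reached before any neutropenia under 5.3.1.3, for example 50% after grade 3 hand-foot syndrome, a second appearance of grade 2 or 3 diarrhea, or grade 4 diarrhea.

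**Restart dose after neutropenia above grade 2 (mg/m², twice daily)**

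| Current dose | 5.3.1.3, dose read as current (0.75 × current) | 5.3.1.4.2 (0.75 × starting) | 5.3.1.4.2 limited by the no-increase sentence |
|---|---|---|---|
| 100% = 825 | 0.75 × 825 = 618.75 | 618.75 | 618.75 |
| 75% = 618.75 | 0.75 × 618.75 = 464.1 | 618.75 | 618.75 |
| 50% = 412.5 | 0.75 × 412.5 = 309.4 | 618.75 | 412.5 |

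- At full dose every reading agrees.
- At 75% the only difference is the meaning of the reference dose. 5.3.1.4.2 leaves the dose unchanged, so it does not breach the no-increase sentence.
- At 50%, 5.3.1.4.2 read literally raises the dose by 618.75 / 412.5 = 1.5 times, against 5.3.1.3. This conflict does not depend on the reference dose in 5.3.1.3. If that reference is the current dose, the two sections are a factor of 618.75 / 309.4 = 2.0 apart.

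**Restart without neutropenia above grade 2.** This is a different event, such as a hold for fever or infection. 5.3.1.4.2 gives 1.00 × 825 = 825. For a patient already at 75% that is 825 / 618.75 = 1.33 times the previous dose; for one at 50%, 825 / 412.5 = 2.0 times. Both are increases that 5.3.1.3 bars.

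**Recovery level**

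| Event | 5.3.1.3 | 5.3.1.4.2 |
|---|---|---|
| Neutropenia | grade 1 | ANC 1,500/mm³, fever or infection resolved |
| Neutropenic fever | grade 0 | ANC 1,500/mm³, fever or infection resolved |

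5.3.1.4.2 uses one count where 5.3.1.3 uses two grades. If grade 0 after neutropenic fever covers the neutrophil count as well as the fever, a single count cannot correspond to both. The grade boundaries are in Appendix B, which was not in the text available for this review, so this cannot be settled here. If 1,500 is the edge of grade 1, the neutropenia rows agree and only the fever row is in question.

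**Entry against restart.** 1,500 − 1,200 = 300/mm³, and 300 / 1,200 = 25%. A patient who enters above 1,200 and below 1,500 must exceed the entry count before 5.3.1.4.2 allows a restart. The removal sentence in 5.3.1.3 does not say whether failing to reach 1,500 counts as not recovering.

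**The case against.** The strongest reply on dose is that the no-increase sentence is a general limit, placed before all the toxicity entries, and silently governs 5.3.1.4.2. The diarrhea and hand-foot entries also give percentages of the starting dose without repeating it, so 5.3.1.4.2 follows the protocol's usual drafting; and it says a patient may restart, which permits rather than orders. This is a reasonable reading. But the text does not state it, and a separately headed special instruction can be read as overriding the general rule.

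Several stronger inferences are tempting and are not supported:

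- **That the sections conflict on dose in general.** They agree for a first event at full dose.
- **That one patient faces three restart doses.** This arises only at 50%, only if the reference dose in 5.3.1.3 is the current dose, and only if the no-increase sentence is counted as a rule of its own. The 100% branch belongs to a different event and is not a further answer.
- **That recovery levels plainly contradict each other.** Without Appendix B this is unproven, and grade 0 may refer to the fever alone.
- **That a patient back at baseline will be removed.** The removal sentence is in 5.3.1.3, where recovery is by grade; 5.3.1.4.2 contains no removal rule. The baseline-shift clause may prevent removal. It is discretionary and framed in grades, so it does not alter the fixed count of 1,500, and the possibility remains. A restart count above the entry count is not in itself a contradiction.
- **That the primary analysis is affected.** Section 5.4 stops the capsules when capecitabine is discontinued, which need not include a temporary hold, and the disputed capecitabine dose does not change the capsule dose. Section 10.1 leaves out of the analysis patients who fail to complete therapy for reasons other than treatment-related toxicity or progression, so stopping for neutropenia is not a ground for exclusion there.

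The affected group may also be small. Treatment runs over 28 fractions, the dose conflict needs a prior reduction, and the background reports less hematologic toxicity in a phase I trial of capecitabine with radiotherapy than expected from infusional 5-FU.

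**Conclusion.** The inconsistency is real but limited to particular patients.

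- **Dose, established from the text.** For a patient at 50% with neutropenia above grade 2, 5.3.1.4.2 read literally gives 618.75 against a current 412.5 mg/m². For any reduced patient held without such neutropenia, it gives 825. Both are increases that 5.3.1.3 forbids.
- **Dose, conditional.** The values 309.4 and 464.1 rest on reading the reference dose in 5.3.1.3 as the current dose.
- **Recovery after neutropenic fever, possible.** It depends on the Appendix B boundaries and on what grade 0 refers to.
- **Removal at the entry count, possible but not certain.** It depends on how recovery is judged and whether the investigator applies the baseline-shift clause. The documents do not give the share of patients entering between 1,200 and 1,500.

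The frequency of all of these is unknown. The case for acting is that the rules govern re-dosing after toxicity and the remedy is cheap. It is not that trial results are shown to be at risk.

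**What to change.** Reconcile sections 4.1.6, 5.3.1.3 and 5.3.1.4.2 in one amendment:

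1. Give neutropenia and neutropenic fever one restart statement each, with one named reference dose (current or starting) and one recovery level, expressed the same way wherever it appears. For neutropenic fever, say whether that level refers to the count, the fever or both.
2. State how each restart statement, including the 100% branch, relates to the no-increase sentence: which governs when they differ for a patient already reduced.
3. State how recovery is judged for a patient whose entry ANC is below the restart count, and make the removal sentence refer to that definition.
4. Replace the duplicate text with a cross-reference.

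The medical lead decides which rule and which values stand; no dose, count or precedence is proposed here. The cost is a wording amendment, with no added visits, tests or patients.

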5.3.1.4.3 Diarrhea

A three-step plan to manage diarrhea will be used. The goal will be to keep the frequency of bowel movements to less than four per day. Patients will initially take Lomotil as needed. When that is no longer sufficient to control the increased frequency of bowel movement, patients take 2 lomotil every 3-4 hours, which is step 2. Subsequently, Imodium is added and alternated with Lomotil, which is step 3; 2 tablets of one or the other is taken every 2-3 hours. Delayed and immediate release narcotics will be used at the discretion of the treating physician. Infectious diarrhea must be considered as an etiology, particularly if diarrhea occurs during the first two weeks of radiation. Outpatient intravenous rehydration will be given in patients who become dehydrated. At the discretion of the treating physician, empiric use of a fluoroquinolone may be considered.

5.3.1.5 Warnings and Precautions

5.3.1.5.1 **Renal Insufficiency:** Patients with moderate renal impairment at baseline require dose reduction (See section 3.2.9.2, Dosage Regimen and Administration.) Patients with mild and moderate renal impairment at baseline should be carefully monitored for adverse events. Prompt interruption of therapy with subsequent dose adjustments will be made if a patient develops a grade 2 to 4 adverse event. Patients will be taken off study if they do not recover. Capecitabine is contraindicated in patients with a creatinine clearance of < 30 ml/min.

5.3.1.5.2 **Pregnancy/Nursing:** Capecitabine may cause fetal harm when given to a pregnant woman. If the drug is used during pregnancy, or if the patient becomes pregnant while receiving this drug, the patient should be apprised of the potential hazard to the fetus. Women of childbearing potential should be advised to avoid becoming pregnant while receiving treatment with capecitabine. Because of the potential for serious adverse reactions in nursing infants from capecitabine, it is recommended that nursing be discontinued when receiving capecitabine therapy.

5.3.1.5.3 **Coagulopathy:** Patients receiving concomitant capecitabine and oral coumarin-derivative anticoagulant therapy should have their anticoagulant response (INR or prothrombin time) monitored frequently in order to adjust the anticoagulant dose accordingly. A clinically important Capecitabine-Warfarin drug interaction was demonstrated in a clinical pharmacology trial. Altered coagulation parameters and/or bleeding, including death, have been reported in patients taking capecitabine concomitantly with coumarin-derivative

anticoagulants such as warfarin and phenprocoumon. Postmarketing reports have shown clinically significant increases in prothrombin time (PT) and INR in patients who were stabilized on anticoagulants at the time capecitabine was introduced. These events occurred within several days and up to several months after initiating capecitabine therapy and, in a few cases, within one month after stopping capecitabine. These events occurred in patients with and without liver metastases. Age greater than 60 and a diagnosis of cancer independently predispose patients to an increased risk of coagulopathy.

- 5.3.1.5.4 **Cardiotoxicity:** The cardiotoxicity observed with capecitabine includes myocardial infarction/ischemia, angina, dysrhythmias, cardiac arrest, cardiac failure, sudden death, electrocardiographic changes, and cardiomyopathy. These adverse events may be more common in patients with a prior history of coronary artery disease.
- 5.3.1.5.5 **General:** This treatment is foreseen as a self-administered out-patient treatment, and in certain circumstances adverse events that could occur, such as diarrhea, or hand-foot syndrome can rapidly become serious. In the case where a patient experiences any toxicity between scheduled visits, the patient will be instructed to contact the clinic as soon as possible, for further directions, discontinuation of study medication, and/or treatment.

